7.10.4 ADVERSE EVENT ASSESSMENT AND RECORDING

The Investigator will probe, via discussion with the subject, for the occurrence of AEs during each subject visit and record the information in the site's source documents. For each AE, the PI should note the start and resolution dates, the severity, whether it meets the definition of an SAE (see Section 7.9.2), the relationship of the event to the study drug, the action taken regarding study drug, and the outcome of the event. Data should be transcribed from the source documents to the CRF as per the CRF instructions.

When reporting an adverse event, the event description should use the best matching terminology describing the event as found in the "Common Terminology Criteria for Adverse Events" (CTCAE, v 4.03). If an available CTCAE term fits the event well, no additional descriptors may be needed.

However, the Investigator should add any necessary descriptions in order to clarify the event or to place it in an appropriate context. If an appropriate term matching the adverse event cannot be found in the CTCAE and you do not know the preferred MedDRA term, the adverse event description should include a diagnosis, sign or

symptom with additional information to facilitate subsequent categorization into MedDRA coding terms

7.10.4.1 INTENSITY

The PI must grade the severity of all reported adverse events into one of five categories: Grade 1 (Mild), Grade 2 (Moderate), Grade 3 (Severe), Grade 4 (Life-Threatening) or Grade 5 (Death related to AE). The standardized CTCAE severity grading scales for the specific type of adverse event reported must be used when a matching CTCAE term is available. If no reference to a standard grading scale applies or is immediately available, use the following guideline:

7.10.4.1.1 GRADE 1 –MILD

Persistence of any otherwise insignificant medical occurrence beyond 72 hours or any transient (< 72 hours) AE considered by the PI to be related to the study drug. No or minimal medical therapy or intervention required, hospitalization not necessary, no or little limitation in normal activities; nonprescription or single-use prescription therapy may be employed to relieve symptoms. Mild adverse events may be listed as expected consequences of the therapy for any given protocol, and standard supportive measures for such an expected event do not necessarily elevate the event to a higher grade.

7.10.4.1.2 GRADE 2- MODERATE

Mild to moderate limitation in activity, some assistance may be needed; possibly none but usually minimal intervention/therapy required, hospitalization possible.

7.10.4.1.3 GRADE 3- SEVERE

Marked limitation in activity, some assistance usually required; medical intervention/therapy required; hospitalization possible or likely. [Specifically, for ocular adverse events in this vision related study, an immediately sight-threatening condition (e.g., impending corneal perforation, retinal detachment) may be categorized as Grade 3 if it would lead to total blindness in the affected eye(s).]

7.10.4.1.4 GRADE 4- LIFE THREATENING

Extreme limitation in activity, significant and immediate assistance required; significant medical/therapy intervention required to prevent loss of life; hospitalization, emergency treatment or hospice care probable. This grade is used when the participant was, in the view of the PI, at substantial risk of dying at the time of the adverse event or it was suspected that use or continued use of the test article would have resulted in the participant's death. (This does not include a reaction that, had it occurred in a more serious form, might have caused death. For example, drug-induced hepatitis that resolved without evidence of hepatic failure would not be considered life-threatening even though drug-induced hepatitis can be fatal.)

7.10.4.1.5 GRADE 5- DEATH

Death related to AE

7.10.4.2 CAUSALITY

The PI (or an authorized study physician) must submit an attribution for causality of the reported adverse event to the test article or procedure.

The attribution should take into account both the temporal association and any known physical, physiological or toxicological information regarding the test article that could reasonably infer causality. Causality should only be considered for the experimental test article and not for any standard study examination or diagnostic procedures. The four attribution categories are:

Unrelated	
Does not follow a reasonable temporal sequence from the administration of study drug.
 
The event or laboratory test abnormality is clearly due to extraneous causes (disease, other drugs, environment, etc.)

Unlikely related	
Does not follow a known pattern of response to study drug.
 
Does not follow a reasonable temporal sequence from the administration of study drug.
 
Disease or other drugs provides plausible explanation.
 
It does not reappear or worsen when study drug is re-administered

Possibly related	
Follows a known pattern of response to study drug.
 
Time sequence from administration of the study drug is reasonable.
 
Could also be explained by disease or other drugs.

Probably related	
Follows a known pattern of response to study drug.
 
Time sequence from administration of the study drug is reasonable.
 
Response to withdrawal clinically reasonable.
 
Cannot be reasonably explained by the known characteristics of the participant's clinical state, environmental factors, or other therapies administered to the subject

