5.2 TREATMENTS ADMINISTERED

5.2.1 DOSE LEVELS AND STUDY ARMS

A single dose of 1- and 2 mg Fludrocortisone acetate/0.1mL will be tested in this study. Subjects will receive 1 IVT injection as outlined in the table below.

	Treatment Arm	Dose Escalation
Part 1	Fludrocortisone acetate 1 mg/0.1mL at Day 0	If no dose limiting toxicity is observed in 3 patients at this given dose level, the dose will be escalated to the following level:
Part 2	Fludrocortisone acetate 2 mg/0.1mL at Day 0	

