7.11.2 EXPECTED AE RELATED TO THE IVT INJECTION PROCEDURE

Mild discomfort related to the injection procedure (including use of an eyelid speculum, anaesthetic drops, mydriatic drops, antibiotic drops, povidone-iodine drops or flush and subconjunctival injection of anaesthetic, as well as the actual insertion of the IVT needle) are expected. These procedure-related adverse events include but are not limited to: redness, mild eye pain, eye irritation, visual disturbance, abnormal sensation in the eye, etc. and will be graded as indicated in Section 7.9.4.

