8.3 ANALYSIS OF PRIMARY SAFETY ENDPOINTS

No formal inferential statistics will be performed on safety assessments. Statistical methods for the safety analyses will be primarily descriptive in nature. The Fludrocortisone acetate 1mg/0.1mL and 2mg/0.1 mL injection will be considered as safe and tolerable based on the number of subjects presenting severe AEs related to the study drug. It is understood that safety is a medical judgment that cannot be prospectively defined in detail. However, as general guidance, a subject will be considered to have tolerated a dose if the subject experiences no clinically significant drug-related adverse event or laboratory abnormality. Conversely, a subject will not be considered to have tolerated the dose if he experiences a clinically significant drug-related adverse event or laboratory abnormality during the study drug administration or post-administration follow-up period.

Listings and summaries for all safety data will be presented using the Safety Population. Descriptive statistics (mean, SD, median, minimum and maximum) will be calculated for summaries of continuous safety data and frequency counts and percentages (where appropriate) will be calculated for summaries of discrete/categorical safety data.

Adverse events (AEs) will be coded using the Medical Dictionary for Regulatory Activities (MedDRA), and data will be summarised by System, Organ, Class and preferred term. The number and percent of participants reporting each AE will be summarised descriptively (n=9). A participant with two or more AEs within the same level of summarisation (i.e., system, organ, class or preferred term) will be counted only once in that level. The number of AEs reported will also be presented. Adverse events will also be summarised by severity as well as relationship to study treatment. A by-participant AE data listing, including verbatim term, preferred term, system organ class, severity, and relationship to study treatment, will be provided. Separate listings will be generated for SAEs and AEs leading to study/treatment discontinuation.

All haematology, blood chemistry and urinalysis (continuous variables) parameters will be summarised using descriptive statistics for all study visits assessed, including change from baseline (last pre-surgery value) for all post-surgery assessments. All laboratory data will be included in the data listings and all test values outside the normal range will be flagged.

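### The causality scale in 7.10.4.2 gives no place to record an injection cause and carries items that a single dose cannot test, so drug-related counts may mix drug and needle effects

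*Protocol*

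**What the plan says.** Section 7.10.4.2 opens by stating that the investigator "must submit an attribution for causality of the reported adverse event to the test article or procedure". The next paragraph says: "Causality should only be considered for the experimental test article and not for any standard study examination or diagnostic procedures". Four categories follow (unrelated, unlikely, possibly and probably related), each worded in terms of study drug.

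Two items in the scale presuppose more than one exposure, or an exposure that can be stopped. Under unlikely related: "It does not reappear or worsen when study drug is re-administered". Under probably related: "Response to withdrawal clinically reasonable". The dosing section, 5.2.1, says: "Subjects will receive 1 IVT injection as outlined in the table below".

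Section 7.11.2 sets out a separate class of expected events from the injection itself, beginning "Mild discomfort related to the injection procedure".

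Relatedness is then used in three ways:

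- Section 6.2 makes the enrolment stop and the move to the second cohort depend on limiting toxicity related to study drug. Its guidance on whether a participant tolerated the dose also turns on drug-related events.
- Section 8.3 repeats that guidance and judges the doses safe and tolerable "based on the number of subjects presenting severe AEs related to the study drug".
- Section 8.3 also tabulates adverse events by relationship to study treatment.

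**The concern.** The ocular events of most interest can come from the needle or from the drug. Section 2.3.3 lists haemorrhage, endophthalmitis and a transient rise in IOP as risks of intravitreal injection. Section 2.2 lists ocular hypertension and endophthalmitis among the complications of intravitreal corticosteroids. The limiting toxicities in 6.2 (inflammation, raised IOP, vision loss, haemorrhage) overlap with both lists.

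The trial is open label and has no control injection, so no between-group comparison can separate the two causes. The investigator's attribution carries much of that burden, and the scale gives no option for the injection. If the field is not collected during the trial, a later analysis plan cannot reconstruct it.

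**Working it through.** The plan gives no figure to reproduce: the sample size has no formal statistical basis, and no error rate is stated for any safety rule. The check is mainly a reading of the text.

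**1. Request against permission.** The opening sentence of 7.10.4.2 names two possible causes. The following paragraph limits the assessment to one of them, and the categories keep to that limit.

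**2. Where would an injection effect go?** Take an eye event soon after dosing that the investigator believes the needle caused.

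| Category | What it asks | Fit for a needle effect |
|---|---|---|
| Unrelated | Implausible timing; clear outside cause, with an open-ended list | Timing is plausible, so the first item fails; the open list might take it |
| Unlikely | No known drug pattern; implausible timing; disease or other drugs as explanation; no recurrence on re-dosing | Timing fails; the needle is not among the explanations |
| Possibly | Known drug pattern; plausible timing; disease or other drugs could also explain it | Timing fits; the needle is not among the explanations |
| Probably | Known drug pattern; plausible timing; reasonable response to withdrawal; no explanation from clinical state, environment or other therapies | Timing fits; the needle is not among the causes to be ruled out |

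No row is written for this event. One assessor could choose unrelated and another possibly related, and both could defend the choice.

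**3. Items against a single dose.** Absence of recurrence on re-dosing is never observed, because there is no second dose. The item therefore cannot discriminate. An injected dose also cannot be withdrawn in the ordinary sense, although it does clear: in the rabbit study in 2.2.3, aggregates disappeared by 22 ± 8 days in the 2 mg group. The withdrawal item is badly worded for this design, but a time-course version of it could be assessed.

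**4. Meaning of related.** The protocol does not say which of the four categories count as drug-related in 6.2 or 8.3, or whether every item in a category must be met.

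**5. Sensitivity of small counts.** One participant reassigned changes an observed proportion by 1/3 = 33.3 points in the first cohort, 1/6 = 16.7 points in the second and 1/9 = 11.1 points overall. Clopper-Pearson 95% intervals are 0–71% for 0/3, 1–91% for 1/3, 0–46% for 0/6 and 0–64% for 1/6. These follow from the cohort sizes alone and would hold for any reclassification on any scale.

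**6. Illustration under assumptions.** Suppose the rule of more than two related limiting toxicities is applied over nine independent participants (8.6 says up to 12). Let p be the chance of a truly drug-caused limiting event and q the share attributed to drug. The chance of exceeding two is P(X ≥ 3), with X binomial (9, p × q).

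| p | q = 1 | q = 0.75 | q = 0.5 |
|---|---|---|---|
| 0.20 | 0.262 | 0.141 | 0.053 |
| 0.30 | 0.537 | 0.330 | 0.141 |
| 0.50 | 0.910 | 0.718 | 0.399 |

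The same arithmetic runs the other way. If the true drug risk is 0.15 and a further 0.15 of needle events are all counted as drug-related, the chance rises from 0.141 to 0.537. Neither p nor q is in the protocol, so the table shows sensitivity and does not estimate an error.

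**The case against.** The sentence in 7.10.4.2 excludes examinations and diagnostic procedures. An intravitreal injection is neither, so the opening sentence may well intend the injection to be assessed. This reading is fair and softens the contradiction. It does not remove it: the restriction to the test article remains, and no category accommodates an injection cause.

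A reader might infer that the scale pushes ratings towards less related. The documents do not support that. An event that fails the withdrawal item under probably related can still be possibly related, which has no such item. The re-administration item is one of several under unlikely related, and nothing says it suffices alone. A needle event with plausible timing may be rated possibly related for want of another option, which would inflate the drug count. The requirement "Follows a known pattern of response to study drug", set although 2.3.3 reports no human intravitreal use, does not settle the direction either, because class complications (2.2) and rabbit data (2.2.3) could supply a pattern.

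A reader might also infer that recorded attribution is the only evidence on cause. It is not. Section 7.8 requires vision and IOP checks within 15 minutes of injection, 7.10.4 records onset, resolution and outcome, and 8.3 promises a listing by participant. With about nine participants, each case can be read individually.

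Much of the safety assessment also carries no causality filter: the count of treatment-emergent events (Synopsis, 3.2.1), the Synopsis definition of limiting toxicity, the escalation table in 5.2.1 and the DSMB criteria in 9.7. That limits the damage. It does not repair the uses in 6.2 and 8.3 that do depend on relatedness. Section 8.3 also calls safety a medical judgment, so the effect on its conclusion is not mechanical.

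**Conclusion.** The point stands in a limited form. Section 7.10.4.2 contradicts itself on what may be attributed, leaves injection causes unrecorded although 7.11.2 recognises them, and includes one item that cannot be observed after a single dose and another that does not apply as worded. Because 6.2 and 8.3 use drug-relatedness and there is no control injection, the drug-related counts may mix drug and needle effects.

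The direction and size of the error cannot be derived from the protocol. The 33- and 17-point shifts show only how much one reassignment would matter, and nothing shows that the wording would move even one participant. All-cause adverse event counts and the data the DSMB reviews are unaffected.

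The conclusion assumes that the CRF follows 7.10.4.2 and has no separate procedure field; the CRF is not shown. The change is worth making before data are collected, because the missing attribution could not be supplied afterwards.

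**What to change.** - In 7.10.4.2 and the CRF, record two attributions for each adverse event: one to FCA and one to the injection procedure. Keep the exclusion for examinations and diagnostic procedures, and state that the injection is not covered by it.
- Delete the re-administration item. Reword the withdrawal item as a time course consistent with clearance of the drug.
- State whether all items in a category must be met, and which categories count as related wherever 6.2 and 8.3 use the term.
- Reconcile the Synopsis, which puts no relatedness condition on limiting toxicity when it describes stopping enrolment, with 6.2, which adds one. Which version applies is for the sponsor and the safety committee to decide.
- Tabulate drug-related, procedure-related and all-cause adverse events by dose.

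The cost is one added CRF field, short protocol wording and one extra summary column. No dose, visit or sample size changes.

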7.10.5 SERIOUS ADVERSE EVENT REPORTING

All SAEs (defined in Section 7.9.2), whether judged related or not to study medication, will be reported to the Sponsor (or designated Medical Monitor) by telephone, e-mail or facsimile within 24 hours of the Investigator becoming aware of such SAEs. The contact details can be found of the serious adverse event form.

The initial SAE Report should include, at a minimum, the following information:

- Protocol number
- Site number
- Subject screening number, initials, gender, and date of birth
- Name of PI and investigator site address
- Details of SAE
- Criterion for classification as “serious”
- Date of SAE onset

Follow-up SAE reports should be submitted as further information becomes available, and the final SAE Report should include information on the SAE intensity, outcome, and relationship to study drug; dates of study drug administration, concomitant medications, and any other relevant information. The PI should also provide clear copies of supporting documents as necessary (e.g. hospital discharge summary, laboratory reports, autopsy reports, etc.), with the subject’s personal identifiers removed. All SAEs will be followed until the acute event has resolved, even if the subject discontinues study participation prior to the resolution. The Investigator must report SAEs occurring at his/her site to the IRB/IEC as required.

7.11 EXPECTED ADVERSE EVENTS

7.11.1 EXPECTED AE RELATED TO THE TEST ARTICLE

No ocular or systemic AE related to the investigational drug are expected at the doses proposed in this protocol.

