1.1 SYNOPSIS

Title:	A Phase 1b, study of safety and tolerability of Intravitreal Fludrocortisone acetate (FCA in Patients with Geographic Atrophy (GA)
Sponsor:	Eye Co Pty Ltd
Protocol Number, Version and Date:	EC-FCA-001/ Version 1.3 / 22 January 2020
Investigational Product, Dose and Route of Administration:	Fludrocortisone acetate (FCA) 1mg/0.1ml & 2mg/0.1ml Intravitreal (IVT) injection
Rationale for dose:	
Single dose of 0.1 ml in a concentration of 1mg/0.1 mL and 2mg/0.1mL was selected based on previous pre-clinical model (Kivilcim et al). There were no signs of retinal toxicity on slit-lamp examination, indirect ophthalmoscopy, or by light microscopy in all eyes injected with 400µg/0.1mL, 1mg/0.1mL and 2mg/0.1mL. However, it was reported 1 case of intravitreal haemorrhage in 4 mg/0.1 mL.
 
Systemic injection of Fludrocortisone acetate has serious mineral corticoid and glucocorticoid side effects such as hypertension, potassium loss, Cushingoid changes, etc. Intravitreal injection fludrocortisone acetate may avoid systemic side effects.

Objectives:	To determine safety and tolerability of a single dose intravitreal (IVT) injection of 1mg/0.1mL and 2mg/0.1mL FCA in subjects

with GA secondary to Age-Related Macular Degeneration (AMD).

Study Population: Study population will comprise of patients with GA secondary to AMD in both eyes with no previous treatment. The study is planned to enrol up to 9 participants.

Study Design: This study is planned to enrol 9 participants to assess dose escalation based on a 3+3 algorithm. Enrolment will stop if > 2 patients experience dose-limiting toxicity at any time during the study. Dose-limiting toxicity is defined by intraocular inflammation, elevated IOP, reduced vision (loss of ≥ 15 letters), or haemorrhage within 28 days after injection.

Part 1 involves a single participant to assess safety and tolerability of 1mg/0.1mL FCA. This participant will be followed for up to 28 days and reviewed by a safety review committee prior to the recruitment of a further 2 participants treated with 1mg/0.1mL FCA totalling in 3 participants in the first cohort.

Part 2 involves a single participant to assess safety and tolerability of 2mg/0.1mL FCA. This participant will be followed for up to 28 days and reviewed by an independent safety review committee prior to the recruitment of a further 5 participants treated with 2mg/0.1mL FCA totalling in 6 participants in the second cohort.

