The presence of drusen and pigmentary abnormalities in the central macula is the main ocular risk factor for late age-related macular degeneration. The greater the area of drusen at the macula the greater the risk of progression to loss of vision. Using the direct ophthalmoscope or a slit lamp these early changes can be detected.

AMD is a highly complex disease that is affected by multiple factors, such as ageing, genetic predisposition, environmental elements, oxidative stress and inflammatory effects [2, 5, 6]. Smoking, age, alcohol consumption, diet and obesity are important risk factors related to oxidative stress [6, 7]. High body mass index, cardiovascular disease, hypertension and a variety of dietary patterns are risk factors less consistently[8]. Several single-nucleotide polymorphisms (SNPs) that confer increased or decreased risk of inflammation have been identified. They include the well-recognized *complement factor H* (CFH), *CX3CR1*, *Toll-like receptor 3* (TLR3), TLR4, and *interleukin 8* (IL-8)[9]. Although AMD is not a classic inflammatory disease, inflammatory cells have an important role in AMD pathogenesis and progression [5, 10, 11]. Evidence has also suggested that some infectious agents are associated with AMD.

Although relatively simple to diagnose through direct visualization augmented with rapid sequence fluorescein angiography, treatment has presented a far greater challenge because the true etiology of AMD is largely unknown [12]. Within the past decade, researchers have introduced many new, potentially promising treatment and prevention

options in an attempt to minimize the damage imparted from AMD. The current standard-of-care for the treatment of exudative AMD are the anti-VEGF agents, such as ranibizumab (Lucentis®), aflibercept (Eylea®) and off-label bevacizumab (Avastin®) [13]. No therapy exists for GA which is usually bilateral and relentlessly progressive. Dexamethasone and triamcinolone acetonide (TA) are the commonly used corticosteroids for macular oedema [14, 15]. Most studies showed their effectiveness in improving vision function and reducing macular oedema. Nevertheless, intravitreal injection of corticosteroids carries significant complication risk such as cataract progression, ocular hypertension and endophthalmitis.

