6.2 SUBJECT ENROLLMENT

It is the responsibility of the investigator to ensure that subjects are eligible to participate in the study prior to enrollment and throughout the study. Documentation of the personally signed and dated informed consent of each subject, using the study-specific ICF, is required before initiating the Screening process. After written informed consent has been obtained and eligibility to participate established, investigative site personnel will obtain the subject's identification number. Only eligible subjects will be allocated to the open label FCA 1 mg/0.1mL or 2mg/0.1 mL.

Enrollment will occur in two parts in order to minimise the likelihood that subjects will be exposed to risks. During part 1 & 2, subjects will be screened one by one as only one patient will initially be enrolled during part 1 of the trial. The first enrolled subject will participate in a screening period of up to 14 days and a follow-up period of 28 days, to detect an IOP response.

After first subject has completed the follow-up of 28 days after FCA 1mg/0.1 mL injection, The subject's safety data will be reviewed the safety data of this will be reviewed by an independent safety review committee to determine whether to commence enrolment of additional 2 patients in the first cohort of 1mg/0.1mL dose of FCA. Enrolment will be stopped if >2 patients experience limiting-toxicity adverse event related to the study drug. If no more than two adverse events considered to be related to the study drug occur with limiting toxicity, the second cohort will be recruited. Dose-limiting toxicity is defined by intraocular inflammation, elevated IOP, reduced vision (loss of ≥ 15 letters), or haemorrhage within 28 days after injection.

Part 2 will take in place if the 3 subjects have tolerated well the dose. Part 2 initially involves a single subject treated with 2mg/0.1mL FCA to assess safety and tolerability. This subject will be followed for up to 28 days and reviewed by an independent safety

review committee prior to the recruitment of a further 5 subjects treated with 2mg/0.1mL FCA totalling in 6 subjects in the second cohort.

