7.10.3 ADVERSE EVENTS OF SPECIAL INTEREST

An adverse event of special interest is one of scientific and medical concern specific to the Sponsor's product or program where ongoing monitoring and rapid communication by the Investigator to the Sponsor may be appropriate. These adverse events may be serious or non-serious. Applicable adverse events may require further investigation in order to characterize and understand, and depending upon the nature of the event, rapid communication by the trial Sponsor to other parties may also be required. These adverse events of special interest must be reported using the same mechanism and timeframe (i.e. within one working day of the Investigator's or delegate's knowledge of the event) as described for serious adverse events in Section 7.9.2. The adverse events of special interest include the following:

- Endophthalmitis
- 4+ ocular inflammation

- 2-3+ ocular inflammation that fails to decrease to 1+ or less within 30 days of the onset of the event
- Sustained (> 5 minutes) loss of light perception after FCA injection
- Sustained elevation of IOP (30 mmHg) at/past 90 minutes' post-injection
- Any elevation of IOP requiring surgical intervention (i.e. paracentesis)
- New vitreous hemorrhage of > 2+ severity that does not resolve within 14 days of the onset of the event
- Cataract progression

If an adverse event of special interest occurs in a study subject, the study subject will be followed for resolution of the adverse event. A decision will be made by the Sponsor concerning further exposure to the study treatment and further participation in the study.

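### Section 7.11.1 expects no drug-related adverse event, against the protocol's own account of steroid risks, and could be read as leaving no known drug pattern for attributing causality

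*Protocol*

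**What the plan says.** - **Protocol 7.11.1** (expected events of the test article): "No ocular or systemic AE related to the investigational drug are expected at the doses proposed in this protocol".
- **Protocol 2.2**, on the class: "intravitreal injection of corticosteroids carries significant complication risk such as cataract progression, ocular hypertension and endophthalmitis".
- **Synopsis (1.1)**, on the systemic route: "Systemic injection of Fludrocortisone acetate has serious mineral corticoid and glucocorticoid side effects such as hypertension, potassium loss, Cushingoid changes, etc". The next sentence says that the intravitreal route may avoid these effects.
- **Protocol 6.2**: the first subject has "a follow-up period of 28 days, to detect an IOP response". Elevated IOP within 28 days is also a component of dose-limiting toxicity (DLT).
- **Protocol 7.10.3**: events of special interest include two IOP items and "Cataract progression".
- **Protocol 7.10.4.2**: one descriptor of the unlikely-related category is "Does not follow a known pattern of response to study drug". The affirmative form of that line is the first descriptor of both the possibly and the probably related categories.
- **Protocol 6.2**, stopping sentence: "Enrolment will be stopped if >2 patients experience limiting-toxicity adverse event related to the study drug".
- **Protocol 6.2 and 8.3**, tolerated-dose guidance: a subject has tolerated the dose if no clinically important event or laboratory abnormality is attributed to the drug.
- **Protocol 8.3**, safety conclusion: the doses are judged safe and tolerable "based on the number of subjects presenting severe AEs related to the study drug".

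**The concern.** The protocol treats a pressure rise and cataract progression as foreseeable consequences of a steroid in the eye, and plans monitoring around them. The one section that sets out which drug effects to expect then lists none.

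A flat statement of this kind can be defended as cautious for expedited reporting, because every related event is then unexpected. It is not cautious for attribution. Where causality turns partly on whether an event fits a known drug pattern, a statement that no drug effect is expected can be taken to mean that there is no pattern to fit. Section 2.3.3 adds a competing explanation, since it names traumatic cataract and transient pressure rise as risks of the injection itself.

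The study is open label at about one site with nine subjects planned, so one reading of the table could shape most of the attributions. The related-event counts in 6.2 and 8.3 would then be too low for the class effects that the protocol itself names.

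**Working it through.** The protocol states no DLT rate and no attribution rate, so there is no figure to reproduce. The check is mainly a comparison of text.

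**Step 1. Is 7.11.1 consistent with the rest?**

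| Section | Content |
|---|---|
| 7.11.1 | No drug-related event expected at the study doses |
| 2.2 | Cataract progression and ocular hypertension are significant risks of intravitreal corticosteroids |
| 1.1, 2.2.1 | The drug has high glucocorticoid activity, so 2.2 applies to it |
| 6.2 | 28-day follow-up of the first subject looks for an IOP response |
| 7.10.3 | IOP elevation and cataract progression are of special interest |
| 2.2.3 | Rabbit IOP normal in all dose groups |
| 2.3.3 | First intravitreal use in humans; unforeseen risks acknowledged |

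Only the rabbit result supports 7.11.1. It does not carry a flat statement for a first intravitreal use in humans.

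**Step 2. Which decisions depend on relatedness?**

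| Rule | Uses relatedness? |
|---|---|
| DLT definition (Synopsis, 6.2) | No |
| Synopsis stopping rule, more than 2 patients | No |
| 5.2.1 escalation, no DLT in 3 patients | No |
| 6.2 stopping sentence, more than 2 patients | Yes |
| 6.2 and 8.3 tolerated-dose guidance | Yes |
| 8.3 conclusion on severe events | Yes |

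The stopping rule thus appears in two forms, one with attribution and one without. Part 2 likewise opens on the absence of any DLT under 5.2.1, but on the three subjects having tolerated the dose under 6.2.

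**Step 3. Where does each effect enter?** Elevated IOP is a DLT component, so it enters every rule above. Cataract is not a DLT component and is reviewed at Day 150, after the 28-day window. It bears mainly on 8.3, and there only if it is graded severe or makes the dose count as not tolerated.

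**Step 4. Illustration only.** Let p be an assumed true rate of a drug-caused limiting event and q an assumed chance that it is recorded as related. Neither is in the protocol. The counted rate is e = p × q.

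- None counted in 3: (1 − e)³. This bears on the tolerated-dose reading, not on 5.2.1.
- No more than 2 counted in 3: 1 − e³.
- More than 2 counted in 9: 1 − Σ C(9,k) eᵏ (1 − e)⁹⁻ᵏ, k = 0 to 2.

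At p = 0.30:

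| q | e | None in 3 | No more than 2 in 3 | More than 2 in 9 |
|---|---|---|---|---|
| 1 | 0.30 | 0.70³ = 34.3% | 1 − 0.027 = 97.3% | 53.7% |
| 0.5 | 0.15 | 0.85³ = 61.4% | 1 − 0.003 = 99.7% | 14.1% |

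Range when q falls from 1 to 0.5:

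| p | None in 3 | No more than 2 in 3 | More than 2 in 9 |
|---|---|---|---|
| 0.1 | 72.9% to 85.7% | 99.9% to 100.0% | 5.3% to 0.8% |
| 0.5 | 12.5% to 42.2% | 87.5% to 98.4% | 91.0% to 39.9% |

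If the 6.2 stopping sentence is applied within the first three subjects, attribution hardly matters. Under the tolerated-dose reading, or if the stopping count runs over all nine, it can matter. The table shows sensitivity and does not predict misattribution.

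**The case against.** A reader might infer that 7.11.1 pushes pressure rises and cataracts into the unlikely-related category and so distorts escalation. The documents do not support that, for four reasons.

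- **No link in the text.** Section 7.10.4.2 does not mention 7.11.1 or expectedness. It lets the investigator draw on any known physiological or toxicological information about the product, which covers steroid class effects. Section 2.2.2 also refers to the Investigator's Brochure, which is not at hand.
- **Descriptors, not tests.** The table does not say that every line must be met, and some lines (re-administration, response to withdrawal) cannot apply to a single injection. The unlikely category also lists an unreasonable time sequence, which an early pressure rise would not meet.
- **Escalation.** The 5.2.1 rule, the Synopsis stopping rule and the DLT definition count an IOP elevation whatever its cause.
- **Other safeguards ignore attribution.** The adverse event endpoint counts all treatment-emergent events, IOP is a secondary endpoint, the data safety monitoring board (9.7) considers an IOP change above 10 mmHg and any reported event, and special-interest events are reported quickly without a causality condition.

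All four stand, and they limit the consequence. They do not remove the disagreement between 7.11.1 and 2.2, nor the use of relatedness in 6.2 and 8.3. The systemic half of 7.11.1 is easier to defend, since the Synopsis says that the intravitreal route may avoid systemic effects.

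**Conclusion.** The concern holds as a minor point. Section 7.11.1 does not agree with 2.2, with the purpose of the follow-up in 6.2, or with the special-interest list in 7.10.3. Through the known-pattern descriptor it could be read in a way that lowers the related-event counts behind the 6.2 stopping sentence, the tolerated-dose guidance and the 8.3 conclusion. Under-attribution is a possibility, not something the protocol shows will happen. Its size cannot be derived, because both the event rate and the misattributed share would have to be assumed. It would be wrong to infer that cataract attribution drives escalation. The firmer inconsistency alongside it is that 6.2 makes the stopping count depend on relatedness while the Synopsis does not.

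**What to change.** 1. In 7.11.1, name IOP elevation and cataract progression as known corticosteroid class effects, in line with 2.2 and 7.10.3.
2. In 7.10.4.2, state that these class effects count as a known pattern of response, and that expectedness is not a criterion for causality.
3. If the sponsor wants every related event treated as unexpected for expedited reporting, say so in a separate sentence on reporting.
4. Reconcile the Synopsis, 5.2.1 and 6.2 on whether a DLT counts regardless of attribution. Which rule applies is for the sponsor to decide.

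The cost is a few sentences in an amendment, with no new data collection. Items 1 to 3 leave doses and procedures unchanged. The downside is that more events may be classed as drug-related.
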